## **2.4. Missing and Partial data**

In general, missing data and partial dates will not be imputed and will be treated as missing. Only partially missing diagnosis and infection dates will be temporarily imputed to calculate the duration of infection and the time since diagnosis (see section 4.2.3). The original, non-imputed, dates will be listed.

To calculate the duration of infection or duration of diagnosis, if the reported date is partially missing, the imputation rules below is to be considered:

- Impute with the first day of the month if only day is missing
- Impute with January 1st if only the year is available
- Leave missing if completely missing

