### 5.2.1.1 Mixed effects model for repeated measures

The main comparisons of interest in the efficacy analyses are:

- to evaluate the efficacy of 24 weeks of JNJ-56136379 monotherapy versus placebo+NA;
- to evaluate the efficacy of 24 weeks of JNJ-56136379+NA versus placebo+NA;
- to evaluate the efficacy of 24 weeks of JNJ-56136379 monotherapy versus JNJ-56136379+NA.

The primary endpoint, Week 24 HBsAg change from baseline, will be analyzed by a comparison of each dose of JNJ-56136379 added to the background NA therapy with the concurrent control arm (placebo + NA), within each of the 4 categories defined by subject population and HBeAg status:

- Low dose (75 mg) of JNJ-56136379+NA with placebo+NA (Part A) in currently not treated HBeAg positive subjects
- Low dose (75 mg) of JNJ-56136379+NA with placebo+NA (Part A) in currently not treated HBeAg negative subjects
- Low dose (75 mg) of JNJ-56136379+NA with placebo+NA (Part A) in virologically suppressed HBeAg positive subjects
- Low dose (75 mg) of JNJ-56136379+NA with placebo+NA (Part A) in virologically suppressed HBeAg negative subjects
- High dose (TBD) of JNJ-56136379+NA with placebo+NA (Part B) in currently not treated HBeAg positive subjects
- High dose (TBD) of JNJ-56136379+NA with placebo+NA (Part B) in currently not treated HBeAg negative subjects
- High (TBD) of JNJ-56136379+NA with placebo+NA (Part B) in virologically suppressed HBeAg positive subjects

---

- High (TBD) of JNJ-56136379+NA with placebo+NA (Part B) in virologically suppressed HBeAg negative subjects

The same comparisons versus placebo+NA as above will also be conducted with JNJ-56136379 monotherapy.

Change from baseline based on log10 transform for quantitative HBsAg, will be analyzed by subject population using mixed effects model for repeated measures [MMRM]) including treatment group, analysis time point (treated as discrete/categorical), their interaction, HBeAg status (in the pooled analysis only), as fixed effects. The covariance structure will include a random intercept at the level of the subject to capture between-subject variability, while within-subject variability will be captured with an unstructured (type=UN) covariance matrix. In case the latter leads to convergence issues, alternative within-subject covariance structures will be considered, in the following hierarchy:

- i) First-order ante-dependence structure (type=ANTE(1)),
- ii) Heterogeneous first-order autoregressive structure (type=ARH(1))

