### APPENDIX 3: SAS CODE FOR THE MMRM MODEL

```
proc mixed data=mod01 (where = (paramcd = 'LGHBSAG' ));  
  by hbeagstat;  
  class avisitn trtlon usubjid;  
  model chg = avisitn trtlon trtlon*avisitn / ddfm=kr2;  
  repeated / type=UN subject=usubjid ;  
run;
```

hbeagstat = HBeAg status at baseline

avisitn = analysis visits

trtlon = Treatment groups

usubjid = subject ID

chg = change from baseline

In case the above leads to convergence issues, alternative within-subject covariance structures will be considered, in the following hierarchy:

```
proc mixed data= mod01 maxopt=1000;  
  by hbeagstat;  
  class avisitn trtlon usubjid;  
  model chg= avisitn trtlon trtlon*avisitn /dist=normal link=identity solution ddfm=kr2;  
  random intercept/subject=usubjid v vcorr;  
  random _residual_ /type=ante(1) subject=usubjid g gcorr;  
  covtest 'int' general 1 0 0 0 0 0 0 0 0 0 0 0 0 0 0 0;  
  covtest 'all var equal' general  
    0 1 -1 0 0 0 0 0 0 0 0 0 0 0 0 0,  
    0 0 1 -1 0 0 0 0 0 0 0 0 0 0 0 0,  
    0 0 0 1 -1 0 0 0 0 0 0 0 0 0 0 0,  
    0 0 0 0 1 -1 0 0 0 0 0 0 0 0 0 0,  
    0 0 0 0 0 1 -1 0 0 0 0 0 0 0 0 0,  
    0 0 0 0 0 0 1 -1 0 0 0 0 0 0 0 0,  
    0 0 0 0 0 0 0 1 -1 0 0 0 0 0 0 0;  
  covtest 'all corr equal' general  
    0 0 0 0 0 0 0 0 0 1 -1 0 0 0 0 0,  
    0 0 0 0 0 0 0 0 0 0 1 -1 0 0 0 0,  
    0 0 0 0 0 0 0 0 0 0 0 1 -1 0 0 0,  
    0 0 0 0 0 0 0 0 0 0 0 0 1 -1 0 0,  
    0 0 0 0 0 0 0 0 0 0 0 0 0 1 -1 0,  
    0 0 0 0 0 0 0 0 0 0 0 0 0 0 1 -1;  
  covtest 'all var&corr equal' general  
    0 1 -1 0 0 0 0 0 0 0 0 0 0 0 0 0,  
    0 0 1 -1 0 0 0 0 0 0 0 0 0 0 0 0,  
    0 0 0 1 -1 0 0 0 0 0 0 0 0 0 0 0,  
    0 0 0 0 1 -1 0 0 0 0 0 0 0 0 0 0,  
    0 0 0 0 0 1 -1 0 0 0 0 0 0 0 0 0,  
    0 0 0 0 0 0 1 -1 0 0 0 0 0 0 0 0,
```

---

```

0      0 0 0 0 0 1 -1    0 0 0 0 0 0,
0      0 0 0 0 0 0 0      1 -1 0 0 0 0,
0      0 0 0 0 0 0 0      0 1 -1 0 0 0,
0      0 0 0 0 0 0 0      0 0 1 -1 0 0,
0      0 0 0 0 0 0 0      0 0 0 1 -1 0,
0      0 0 0 0 0 0 0      0 0 0 0 1 -1 0,
0      0 0 0 0 0 0 0      0 0 0 0 0 1 -1;
run;

proc mixed data= mod01 maxopt=1000;
by hbeagstat;
class avisitn trtlon usubjid;
model chg= avisitn trtlon trtlon*avisitn /dist=normal link=identity solution ddfm=kr2;
random intercept/subject=usubjid v vcorr;
random _residual_ /type=arh(1) subject=usubjid g gcorr;
covtest 'int' general 1 0 0 0 0 0 0 0 0;
covtest 'corr' general 0 0 0 0 0 0 0 0 1;
covtest 'all var equal' general
      0      1 -1 0 0 0 0 0 0 ,

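### The MMRM code in SAP Appendix 3 does not index the covariance by visit, so a missed visit followed by a later one can misalign it and give a wrong Week 24 standard error, in either direction.

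*SAP*

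**What the plan says.** SAP section 5.2.1.1 models change from baseline in log10 HBsAg with treatment, time point (categorical) and their interaction, and states that "within-subject variability will be captured with an unstructured (type=UN) covariance matrix". If that fit does not converge, ANTE(1), ARH(1) and AR(1) follow in that order.

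SAP Appendix 3 prints the code. Visit is declared in "class avisitn trtlon usubjid" and enters the MODEL statement, but the covariance statement is "repeated / type=UN subject=usubjid", with no repeated effect. The first fallback uses "random _residual_ /type=ante(1) subject=usubjid g gcorr", and the ARH(1) and AR(1) fallbacks follow the same pattern, so none of the four calls names the visit in its residual covariance.

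On gaps, SAP section 2.4 says that "missing data and partial dates will not be imputed and will be treated as missing". SAP section 2.3 assigns actual visits to contiguous windows and keeps one measurement per subject and time point. Neither section says whether the dataset `mod01` holds a row for a visit that did not take place, or how it is sorted.

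**The concern.** When the repeated effect is empty, PROC MIXED takes a subject's first record as position 1 of the covariance matrix, the second as position 2, and so on. That equals the visit order only if every subject has a row for every visit up to the last one observed, sorted by visit. A subject with a gap and no row for it is shifted from the gap onward.

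The means are not mislabelled: `avisitn` is still a fixed effect, so the Week 24 LS mean belongs to Week 24. What changes is the variance and correlation attached to the shifted records, hence the weights, the standard error, the confidence interval and the p-value. If the UN call runs, nothing in the output would show this.

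The SAP lists this model under the primary endpoint (sections 5.2.1 and 5.2.1.1) and reuses it for other viral markers under section 5.3. It is also run by HBeAg status, where the planned placebo+NA cells have 3 to 7 subjects (protocol Table 7), so one shifted subject is a large part of an arm.

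**Working it through.** The documents state no MMRM standard error, so there is no figure of the plan's to reproduce.

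**Dimension.** The ANTE(1) contrasts in Appendix 3 carry 16 parameters: 1 intercept + 8 variances + 7 correlations. That fits eight visits (Weeks 1, 2, 4, 8, 12, 16, 20, 24). An 8 × 8 unstructured matrix has 8 × 9 / 2 = 36 parameters.

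**Alignment.** Take a subject who misses only Week 2, with no row for it.

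| Record | Actual visit | Covariance position used | Visit at that position in a complete subject |
|---|---|---|---|
| 1 | Week 1 | 1 | Week 1 |
| 2 | Week 4 | 2 | Week 2 |
| 3 | Week 8 | 3 | Week 4 |
| ... | ... | ... | ... |
| 7 | Week 24 | 7 | Week 20 |

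Complete subjects, and subjects who simply stop early, keep the right positions.

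**How many subjects.** The documents give no skip rate. If each of the seven visits before Week 24 is skipped independently with probability p, the share with at least one gap is 1 − (1 − p)^7: 13% at p = 0.02, 30% at 0.05 and 52% at 0.10. Protocol section 3.1 has 70 untreated subjects per part, 3:1:3, with about 60% HBeAg-negative: 70 × 0.6 = 42, or 18:6:18. At p = 0.05 about 6 × 0.30 = 1.8 of the 6 placebo+NA subjects would have a gap.

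**Size if the SD grows.** Assumptions: rows for skipped visits absent, Week 24 SD 0.4 (Table 7, placebo+NA), no true difference, SD rising to Week 24, adjacent correlation 0.9. The model was fitted twice to each dataset, by visit and by record order, and the two-sided 5% rejection rate was taken at Week 24.

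| Layout, skip rate | By record order | By visit |
|---|---|---|
| 10 vs 30, 2% | 7.4% | 5.3% |
| 10 vs 30, 5% | 10.3% | 5.3% |
| 10 vs 30, 10% | 15.5% | 5.2% |
| 10 vs 30, 5% (separate program) | 10.0% | 4.3% |
| 6 vs 18, 5% (separate program) | 10.2% | 4.0% |

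The first three rows use 1,000 replicates (Monte Carlo SE at 10.3%: √(0.103 × 0.897 / 1000) = 1.0 point). The last two use 400 (at 10.0%: √(0.10 × 0.90 / 400) = 1.5 points). For 10 vs 30 at 5%, the mean record-order SE was 0.135 against a true SD of the estimate of 0.165, a ratio of 0.82. Other shapes with growing or constant SD gave 7.7% to 13.5% in the first program. In the second, flat SD gave 6.5% against 4.3%, and SD shrinking by one third gave 5.8% against 4.3%.

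**Direction.** A third simulation used three arms of 40, 120 and 120 to reduce small-sample noise, and compared the mean record-order SE with the mean visit-indexed SE.

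| Assumed SD over visits | 5% skipped | 15% skipped |
|---|---|---|
| Grows as √time | 0.954 | 0.895 |
| Mild growth | 0.982 | 0.955 |
| Flat, AR correlation | 0.991 | 0.978 |
| Flat, exchangeable | 0.993 | 0.988 |
| Mild shrinkage | 1.002 | 1.006 |
| Strong shrinkage | 1.050 | 1.114 |
| Week 24 SD half of earlier visits | 1.110 | 1.270 |

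The visit-indexed SE was 0.96 to 1.06 of the empirical SD throughout. At 6, 18 and 18 with 5% skipped, the record-order SE averaged 2% to 6% lower in the five patterns tried, but was larger in 9% to 33% of replicates. Strong shrinkage was not tried at that size. These ratios compare SE with SE; they leave out that misalignment also makes the estimate itself more variable, which the rejection rates include.

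None of these fits applied Kenward-Roger, which the printed code requests.

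**The case against.** **The dataset may already protect the analysis.** If `mod01` holds a sorted row for every visit with missing `chg`, positions are preserved and the omission does no harm. This stands as a condition: one might infer that every subject with a skipped visit is misaligned, but it takes an absent (or unsorted) row and a later observed visit. The SAP neither creates such rows nor rules them out, and the contiguous windows mean that a visit a few days early or late usually still fills a slot.

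**The direction is not established.** A reader might infer that the Week 24 SE is simply too small. Growing variance is plausible: the protocol's background reports no notable HBsAg change after 28 days, while Table 7 plans Week 24 SDs of 0.4 to 0.6 on placebo+NA and 2.16 on the combination. But the documents give no SD before Week 24 and no within-subject correlations, and the ratios above reverse under strong shrinkage.

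**The 10% is not this trial's error rate.** It rests on an assumed skip rate, SD path and correlation. The 10 vs 30 layout fits the virologically suppressed arms pooled over HBeAg status; for untreated subjects it leaves out the monotherapy arm, which would help estimate the covariance. That Kenward-Roger would act alike on both fits was not shown.

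**The role is limited.** Protocol section 11.3.1 makes the Bayesian comparison the primary analysis and section 11.3.3 places the repeated-measures model among other analyses. No formal testing is planned (protocol section 2.2, SAP section 1.4). All of this stands, but the SAP still reports intervals and p-values from this model under the primary endpoint.

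**Conclusion.** The concern holds in a conditional form. The UN call indexes the covariance by record order, which departs from what section 5.2.1.1 evidently intends. Unless each subject has a sorted row for every visit, a gap followed by a later visit gives the Week 24 difference a wrong SE and interval.

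Under growing SD and 5% skipped visits, the two-sided error rate is about 10% instead of about 4-5%. With flat SD the effect is smaller, and with strongly shrinking SD the SE is too large. The size depends on assumptions that the documents do not settle.

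The three fallbacks have a further problem. They put PROC GLIMMIX syntax (`random _residual_`, `covtest`, `dist=` and `link=`, `maxopt=`) under PROC MIXED, so as printed they should stop with errors. It would therefore be wrong to infer that they misalign silently, or that one added word repairs them.

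The Bayesian analysis (Appendix 1) and the dose-response test (Appendix 2) are unaffected.

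**What to change.** In the first call of Appendix 3, write `repeated avisitn / type=UN subject=usubjid;`.

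Rewrite the ANTE(1), ARH(1) and AR(1) fallbacks in one valid procedure with visit as the residual effect: in PROC MIXED, `repeated avisitn / type=... subject=usubjid;`, or in PROC GLIMMIX, `random avisitn / residual type=... subject=usubjid;`. Carry the same change into the pooled version that adds HBeAg status.

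With visit named, alignment no longer depends on placeholder rows or sort order. A sentence on the structure of `mod01` would still help.

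The cost is one word in the UN call and a short rewrite and test run of three fallbacks. No new data are needed and no power is lost. With complete or early-stopping subjects in sorted order, the UN results do not change.

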#### **APPENDIX 4: DIVISION OF AIDS (DAIDS) TOXICITY GRADING SCALE FOR DETERMINING THE SEVERITY OF ADVERSE EVENTS, MARCH 2017**

See reference  above

---

## APPENDIX 5: TIME AND EVENTS SCHEDULE – SCREENING AND TREATMENT PHASE

Phase	Screening	Treatment ee,kk										Treatment Extension ee,kk						
		Day (D)/Week (W)	<Day -56	D1 a	W1	W2	W4	W8	W12	W16	W20	W24	W28	W32	W36	W40	W44	W48
Study Procedure																		
Screening/Administrative																		
Informed consent form (ICF) b		X																
ICF for optional pharmacogenomic samples		X																
Demographics		X																
Medical and surgical history		X																
Inclusion/exclusion criteria c		X																
Liver biopsy or Fibroscan d		X																
Ultrasound e		X																
Clinical status	X		X f															
Follicle-stimulating hormone test (postmenopausal women only)		X																
Serum pregnancy test (women of childbearing potential only)		X																
Testing for hepatitis A, B, C, D, and E virus and HIV-1 and -2		X																
HBV genotype g		X																
Visit with overnight stay h			X						X									
Check for eligibility for extension phase											X ff	X ff,gg						
Study Treatment Administration																		
Randomization				X														

Phase	Screening	Treatment ee,kk										Treatment Extension ee,kk						
		Day (D)/Week (W)	<Day -56	D1 a	W1	W2	W4	W8	W12	W16	W20	W24	W28	W32	W36	W40	W44	W48
Study Procedure																		
Dispense study medication		X			X	X	X	X	X	X	X hh	X	X	X	X	X	X ii	
Administer study medication i		X	X	X	X	X	X	X	X	X	X	X	X	X	X	X	X	
Distribute diary j						X			X									
Collect diary j								X			X							
Safety Evaluations																		
Complete physical examination k		X									X							
Symptom-directed physical examination l		X	X	X	X	X	X	X	X	X	X	X	X	X	X	X	X	
Vital signs m		X	X	X	X	X	X	X	X	X	X	X	X	X	X	X	X	
Triplelicate 12-lead ECG n		X	X			X		X			X			X			X	
Clinical Laboratory Tests																		
Hematology		X	X	X	X	X	X	X	X	X	X	X	X	X	X	X	X	
Blood chemistry o,p		X	X	X	X	X	X	X	X	X	X	X	X	X	X	X	X	
Blood coagulation		X	X	X	X	X	X	X	X	X	X	X	X	X	X	X	X	
Urinalysis q		X	X	X	X	X	X	X	X	X	X	X	X	X	X	X	X	
Alpha-fetoprotein		X																
Urine pregnancy test (women of childbearing potential only)			X	X	X	X	X	X	X	X	X	X	X	X	X	X	X	
Efficacy Evaluations																		
Fibroscan r				X								X					X	
HBV Virology																		
HBV DNA and HBV RNA ii		X	X	X	X	X	X	X	X	X	X	X	X	X	X	X	X	
Viral genome sequencing s		X	X		X	X	X	X	X	X	X	X	X	X	X	X	X	
HBV Serology																		
Anti-HBs and anti-HBe		X	X										X				X	
HBsAg and HBeAg t (qualitative)		X	X									X					X	

Phase	Screening	Treatment ee,kk										Treatment Extension ee,kk					
		Day (D)/Week (W)	<Day -56	D1 a	W1	W2	W4	W8	W12	W16	W20	W24	W28	W32	W36	W40	W44
Study Procedure																	
HBsAg and HBeAg u (quantitative)		X	X	X	X	X	X	X	X	X	X	X	X	X	X	X	X
HBcrAg jj		X	X	X	X	X	X	X	X	X	X	X	X	X	X	X	X
Exploratory serology v			X		X	X	X	X	X	X	X	X	X	X	X	X	X
Pharmacokinetics																	
Blood sampling for pharmacokinetics of JNJ-56136379 and/or NA (sparse) w			X	X	X	X	X	X			X	X	X	X	X	X	X
Blood sampling for pharmacokinetics of JNJ-56136379 and/or NA (semi-rich) (selected sites only) x			X						X								
Urine collection for pharmacokinetics of JNJ-56136379 and/or NA (selected sites only) y			X z						X								
Blood sampling for exploratory pharmacokinetics of hormonal contraceptives and their metabolites (women on hormonal contraceptives only dd )			X						X		X	X					
Exploratory Biomarkers																	
Host mRNA				X	X	X	X	X	X		X	X	X	X	X		X
Serum proteins				X	X	X		X	X	X	X	X	X	X	X	X	X
Immune cells (PBMCs) (selected sites only) aa			X			X		X			X						X
Pharmacogenomics (DNA)																	
Exploratory host genotyping (optional) bb				X													
Patient-reported Outcome Evaluationsa																	
EQ-5D-5L					X			X					X				
HBQOL					X			X				X					

Phase	Screening	Treatment ee,kk										Treatment Extension ee,kk					
		Day (D)/Week (W)	<Day -56	D1 a	W1	W2	W4	W8	W12	W16	W20	W24	W28	W32	W36	W40	W44
Study Procedure																	
MOS-CFS Cog-R				X				X				X					
SF-36v2				X				X				X					
Ongoing Participant Review																	
Concomitant therapy				X	X	X	X	X	X	X	X	X	X	X	X	X	X
Adverse events				X	X	X	X	X	X	X	X	X	X	X	X	X	X

- a. Day 1 samples are to be collected before the first dose of study drugs.
- b. The ICF must be signed before the first study-related activity.
- c. Minimum criteria for the availability of documentation supporting the eligibility criteria are described in Section **Error! Reference source not found.. C** heck clinical status again before first dose of study medication.
- d. Liver disease staging assessments will be performed by means of a liver biopsy or Fibroscan during the screening period in case not performed within 1 year (in case of liver biopsy) or 6 months (in case of Fibroscan) prior to screening.
- e. Subjects must have absence of signs of hepatocellular carcinoma (HCC) on an abdominal ultrasound performed within 2 months prior to screening or at the time of screening. In case of suspicious findings on conventional ultrasound the subject may still be eligible if HCC has been ruled out by a more specific imaging procedure (contrast enhanced ultrasound, computed tomography [CT] or magnetic resonance imaging [MRI]).
- f. If a subject's clinical status changes (including any available laboratory results or receipt of additional medical records) after screening but before the first dose of study drugs is given such that he or she no longer meets all eligibility criteria, then the subject should be excluded from (further) participation in the study.
- g. HBV genotype will be determined at screening using standard genotyping assay if HBV DNA levels are sufficiently high. In virologically suppressed subjects, available historical data on previous HBV genotype assessment will be collected in the eCRF. Exploratory genotyping assays might be performed.
- h. Only applicable to subjects undergoing semi-rich pharmacokinetic and 24-hour urine sampling (pharmacokinetic subgroup).
- i. Study drugs should be taken in the morning at approximately the same time each day, together with breakfast, except for ETV which should be taken on an empty stomach. At each study visit, the study drugs should be taken on site under the supervision of the study staff. The time of study drug intake should be recorded.
- j. A subject diary will be provided to the subjects in the pharmacokinetic subgroup, and female subjects using hormonal contraceptives. These subjects should report the times of study drug intake at home for 1 week prior to their Week 12 and Week 24 visits in this diary.
- k. Complete physical examination, including height, body weight, temperature, skin examination, and other body systems.

---

- l. Symptom-directed physical examination, including body weight and temperature.
- m. Vital signs include supine systolic blood pressure (SBP), diastolic blood pressure (DBP), and pulse rate.
- n. If blood sampling or vital signs measurement is scheduled for the same time point as ECG recording, the procedures should preferably be performed in the following order: ECG(s), vital signs, blood draw.
- o. Biochemistry samples must be taken fasted for at least 10 hours for measurement of phosphorus, calcium, creatinine clearance, and lipids. Subjects should bring their study drug with them to each visit and have that day's intake at the site.
- p. Creatinine clearance (estimated by the estimated Glomerular Filtration Rate [eGFR], which is calculated by the Modification of Diet in Renal Disease [MDRD] formula) will be assessed.
- q. In case a of positive dipstick result, a urine sample will be set aside for additional examination of the positive parameter (eg, quantification as applicable).
- r. Only applicable to subjects in the pharmacokinetic subgroup and subjects enrolled at a site with an on-site Fibroscan device.
- s. Sequencing on Day 1 (predose) will be performed by default if HBV DNA levels are within the ranges required for the sequencing assay; other samples may be sequenced based on the sponsor virologist's request.
- t. In virologically suppressed subjects, available historical data on HBeAg status before start of NA treatment will be collected in the eCRF.
- u. Quantitative HBeAg assessment will only be performed in subjects who are defined HBeAg-positive at screening based on a qualitative HBeAg assay.
- v. Exploratory serology samples may be analyzed at the sponsor's discretion. Samples may be used to assess virologic or serologic markers of HBV.
- w. Sparse pharmacokinetic sampling will be performed for all subjects. One sample predose at all indicated time points (except on Day 1: one sample 2 hours postdose only). Study drug should be taken on site. The time of study drug intake will be recorded.
- x. Approximately 35% of all subjects (at selected sites only) will undergo semi-rich pharmacokinetic sampling (pharmacokinetic subgroup) predose and 2, 4, 12, and 24 hours postdose. The study drug should be taken on site. The time of study drug intake will be recorded.
- y. Approximately 35% of all subjects (at selected sites only) will have 24-hour urine sampling (pharmacokinetic subgroup) during the intervals 0-2, 2-12, and 12-24 hours postdose. This sampling schedule will require an overnight stay on site.
- z. Applicable to Treatment Arms 4-5 and 9-10 only.
- aa. Immune cell samples (peripheral blood mononuclear cells [PBMC]) may be collected (selected sites only).
- bb. The pharmacogenomic (DNA) sample should preferably be collected at baseline. This sample is optional and will only be collected from subjects who consent separately to this component of the study.
- cc. PRO assessments will be performed by subjects at sites where appropriate translations are available. Subjects will complete the 5-level EuroQol 5-Dimension (EQ-5D-5L), Hepatitis B Quality of Life Instrument (HBQOL), Medical Outcomes Study Cognitive Functioning Scale-Revised (MOS-CFS Cog-R), and Short Form 36 version 2 (SF-36v2) on an electronic device during the specified study visits. The PRO assessments are preferably to be completed immediately after dosing.
- dd. For women on stable ( $\geq 3$  months) hormonal contraceptive treatment at screening, as well as women starting hormonal contraceptive treatment during the study, in which case the first blood sampling should occur at the next scheduled visit.
- ee. All study visits are to be scheduled relative to the baseline visit date and are to occur at the end of Weeks 1, 2, 4, 8, 12, 16, 20, 24, 28, 32, 36, 40, 44 and 48. The visit window is  $\pm 2$  days of the protocol-specified date at Weeks 2-4,  $\pm 5$  days of the protocol-specified date through Week 48.
- ff. Eligibility to enter the treatment extension phase will be determined at Week 20 and Week 24 of the initial 24-week treatment phase, ie, subjects must have completed the initial 24 weeks of treatment and must have achieved a virologic response by Week 20 (HBV DNA  $<$  LLOQ of the HBV DNA assay) without experiencing any safety concerns precluding continued study drug treatment as determined by the investigator.

---

- gg. Subjects enrolled in the study before the Amendment 2 came into effect will need to consent separately for participation in the extension phase. Subjects choosing not to participate in the extension phase will complete their assigned 24-week treatment after which they will enter the 24-week follow-up period. Subjects who are enrolled after the Amendment 2 came into effect will consent to the possible treatment extension by signing the ICF at the start of the study.
- hh. Dispensing of JNJ-56136379/placebo is only applicable for subjects who will enter the treatment extension phase. NA will be dispensed for subjects starting or continuing NA treatment in the treatment extension phase or the follow-up phase.
- ii. Only applicable for subjects who do not meet the treatment completion criteria and start or continue NA treatment. No JNJ-56136379/placebo will be dispensed.
- jj. HBcrAg and HBV RNA samples may be batched and only selected samples may be tested. Samples can be used for assessment of other serologic/virologic markers of HBV.
- kk. Subjects who discontinue treatment early will have an early treatment withdrawal visit and will enter follow-up (see Schedule 1) unless they withdraw consent. Subjects who withdraw consent will be offered an optional safety follow-up visit

